### **11.2 Institutional Review Board (IRB) Approval and Consent**

It is expected that the IRB will have the proper representation and function in accordance with federally mandated regulations. The IRB must approve the consent form and protocol.

In obtaining and documenting informed consent, the investigator should comply with the applicable regulatory requirement(s), and should adhere to Good Clinical Practice (GCP) and to ethical principles that have their origin in the Declaration of Helsinki.

Before recruitment and enrollment onto this study, the subject will be given a full explanation of the study and will be given the opportunity to review the consent form. Each consent form must include all the relevant elements currently required by the FDA Regulations and local or state regulations. Once this essential information has been provided to the subject and the investigator is assured that the subject understands the implications of participating in the study, the subject will be asked to give consent to participate in the study by signing an IRB-approved consent form.

Prior to a patient's participation in the trial, the written informed consent form should be signed and personally dated by the subject and by the person who conducted the informed consent discussion.

### **11.3 Registration Procedures**

All subjects must be registered with the Clinical Research Office before enrollment to study. Prior to registration, eligibility criteria must be confirmed with the Clinical Research Office Study Coordinator or Manager. To register a subject, call [name] Monday through Friday, 9:00AM-5:00PM.

### **11.4 Data Management and Monitoring/Auditing**

Trial monitoring will be conducted no less than annually and refers to a regular interval review of trial related activity and documentation performed by the DOT, which includes but is not limited to accuracy of case report forms, protocol compliance, timeliness and accuracy of Velos entries and AE/SAE management and reporting. Documentation of trial monitoring will be maintained along with other protocol related documents and will be reviewed during internal audit.

Toxicity review will be performed at the annual monitoring review. These reviews will be documented by a written audit report, within 2 weeks of audit completion. The findings are reviewed with the research team to review any discrepancies and discuss corrective action. Audit reports and responses are distributed for review to the Deputy Director of the Cancer Center, DSMC Chairman, PI, DOT Leader and Associate Director of the CRO.

The DOT will review all local serious adverse events and unanticipated problems at monthly DOT research meetings. The discussion of such events is documented in the meeting minutes. Events are reported by the research coordinator to the DSMC per the DSMC plan.

The UTSW Simmons Cancer Center (SCC) Data and Safety Monitoring Committee (DSMC) is responsible for overall monitoring of data quality and patient safety. As part of that responsibility, the DSMC reviews all local serious adverse events and unanticipated problems in real time as they are reported and reviews adverse events on a quarterly basis. The Quality Assurance activity of the Clinical Research Office provides for periodic auditing of clinical research documents to ensure data integrity and regulatory compliance based on risk.

The SCC-DSMC meets quarterly and conducts annual comprehensive reviews of ongoing clinical trials, for which it is the DSMC of record.

Further detail may be found in the SCC-DSMC Plan.

## **11.5 Adherence to the Protocol**

Except for an emergency situation in which proper care for the protection, safety, and well-being of the study subject requires alternative treatment, the study shall be conducted exactly as described in the approved protocol.

### **11.5.1 Emergency Modifications**

Investigators may implement a deviation from, or a change of, the protocol to eliminate an immediate hazard(s) to trial subjects without prior IRB approval.

For any such emergency modification implemented, an IRB modification form must be completed within five (5) business days of making the change.

### **11.5.2 Other Protocol Deviations/Violations**

All other planned deviations from the protocol must have prior approval by the Principal Investigator and the IRB. According to the IRB, a protocol deviation is any unplanned variance from an IRB approved protocol that:

- Is generally noted or recognized after it occurs
- Has no substantive effect on the risks to research participants
- Has no substantive effect on the scientific integrity of the research plan or the value of the data collected
- Did not result from willful or knowing misconduct on the part of the investigator(s).

An unplanned protocol variance is considered a violation if the variance:

- Has harmed or increased the risk of harm to one or more research participants.
- Has damaged the scientific integrity of the data collected for the study.
- Results from willful or knowing misconduct on the part of the investigator(s).
- Demonstrates serious or continuing noncompliance with federal regulations, State laws, or University policies.

If a deviation or violation occurs without prior approval from the Principal Investigator, please follow the guidelines below:

**Protocol Deviations:** Personnel will report to any sponsor or data and safety monitoring committee in accordance with their policies. Deviations should be summarized and reported to the IRB at the time of continuing review.

**Protocol Violations:** Study personnel should report violations within two (2) weeks of the investigator becoming aware of the event using the same IRB online mechanism used to report Unanticipated Problems.

STU042015-076, [name], FormA-ResearchProtocol-V6, Mod\_19, 04-09-20 (1)

CONFIDENTIAL

This material is the property of the [UTSW Simmons Cancer Center](#). Do not disclose or use except as authorized in writing by the study sponsor.

### **11.6 Amendments to the Protocol**

Should amendments to the protocol be required, the amendments will be originated and documented by the Principal Investigator. A summary of changes document outlining proposed changes as well as rationale for changes, when appropriate, is highly recommended. When an amendment to the protocol substantially alters the study design or the potential risk to the patient, a revised consent form might be required.

The written amendment, and if required the amended consent form, must be sent to the IRB for approval prior to implementation.

### **11.7 Record Retention**

Study documentation includes all Case Report Forms, data correction forms or queries, source documents, Sponsor-Investigator correspondence, monitoring logs/letters, and regulatory documents (e.g., protocol and amendments, IRB correspondence and approval, signed patient consent forms).

Source documents include all recordings of observations or notations of clinical activities and all reports and records necessary for the evaluation and reconstruction of the clinical research study.

Government agency regulations and directives require that the study investigator retain all study documentation pertaining to the conduct of a clinical trial. In the case of a study with a drug seeking regulatory approval and marketing, these documents shall be retained for at least two years after the last approval of marketing application in an International Conference on Harmonization (ICH) region. In all other cases, study documents should be kept on file until three years after the completion and final study report of this investigational study.

### **11.8 Obligations of Investigators**

The Principal Investigator is responsible for the conduct of the clinical trial at the site in accordance with Title 21 of the Code of Federal Regulations and/or the Declaration of Helsinki. The Principal Investigator is responsible for personally overseeing the treatment of all study patients. The Principal Investigator must assure that all study site personnel, including sub-investigators and other study staff members, adhere to the study protocol and all FDA/GCP/NCI regulations and guidelines regarding clinical trials both during and after study completion.

The Principal Investigator at each institution or site will be responsible for assuring that all the required data will be collected and entered onto the Case Report Forms. Periodically, monitoring visits may be conducted and the Principal Investigator will provide access to his/her original records to permit verification of proper entry of data. At the completion of the study, all case report forms will be reviewed by the Principal Investigator and will require his/her final signature to verify the accuracy of the data.

### 13.0 Appendices

#### 13.1 Appendix 1: List of prohibited concomitant medications and concomitant medications requiring caution for ceritinib

**Table 14-1 Prohibited medications that are strong inducers or inhibitors of CYP3A, or CYP3A substrates with narrow therapeutic index, or sensitive CYP2C substrates with narrow therapeutic index\*\***

CYP2C8 substrates with narrow therapeutic index			
Paclitaxel			
CYP2C9 substrates with narrow therapeutic index			
Warfarin	phenytoin		
CYP3A4/5 substrates with narrow therapeutic index			
astemizole*	diergotamine	pimozide	alfentanil
cisapride*	ergotamine	quinidine*	terfenadine*
cyclosporine	fentanyl	tacrolimus	sirolimus
Strong CYP3A4/5 inhibitors			
Macrolide antibiotics:	Antivirals:	Antifungals:	Others:
clarithromycin	indinavir	itraconazole	conivaptan
telithromycin	lopinavir	ketoconazole	elvitegravir
troleandomycin	nelfinavir	posaconazole	mibefradil
	ritonavir	voriconazole	nefazodone
	saquinavir		
	tipranavir		
Strong CYP3A/5 inducers			
avasimibe	carbamazepine	phenobarbital	Phenytoin
rifabutin	rifampin	St. John's wort	

\* Compounds with risk of QT prolongation

For an updated list of CYP2C substrates, CYP3A substrates, inhibitors and inducers, please reference the Novartis Oncology Clinical Pharmacology internal memo: drug-drug interactions (DDI) database, Oct 2010, which is compiled primarily from the FDA's "Guidance for Industry, Drug Interaction Studies", the Indiana University School of Medicine's Drug Interactions Database, and the University of Washington's Drug Interaction Database.

\*\*Sensitive substrates: Drugs that exhibit an AUC ratio (AUCi/AUC) of 5-fold or more when co-administered with a known potent inhibitor.

Substrates with narrow therapeutic index (NTI): Drugs whose exposure-response indicates that increases in their exposure levels by the concomitant use of potent inhibitors may lead to serious safety concerns (e.g., Torsades de Pointes).

**Table 14-2 List of medications to be used with caution**

CYP2B6 substrates			
cyclophosphamide	ifosfamide	thiotepa	Bupropion
efavirenz	methadone		
CYP2C8 substrates			
amodiaquine	cerivastatin	repaglinide	Rosiglitazone
torsemide			
CYP2C9 substrates			

---

losartan	irbesartan	diclofenac	ibuprofen
piroxicam	tolbutamide	glipizide	acenocoumarol
celecoxib	sulfamethoxazole	tolbutamide	torsemide

---

CYP3A4/5 substrates			
dronedarone	capravirine	aripiprazole	casopitant
alprazolam	ritonavir	haloperidol	quinine
diazepam	telaprevir	imatinib	tamoxifen
amlodipine	atorvastatin	nilotinib	tolvaptan
diltiazem	everolimus	methadone	trazodone
nifedipine	clarithromycin	boceprevir	vincristine
nisoldipine	erythromycin	brecanavir	verapamil
nitrendipine	telithromycin		
Moderate CYP3A4/5 inhibitors			
ciprofloxacin	darunavir	grapefruit juice	dronedarone
erythromycin	fosamprenavir	aprepitant	tofisopam
amprenavir	diltiazem	casopitant	
atazanavir	verapamil	cimetidine	
Moderate CYP3A4/5 inducers			
bosentan	efavirenz	etravirine	modafinil
nafcillin	ritonavir	talviraline	tipranavir
Proton pump inhibitors			
esomeprazole	lansoprazole	omeprazole	Pantoprazole
rabeprazole			

This database of CYP 2B6, 2C8, 2C9 and 3A4/5 substrates, 3A4/5 inhibitors and inducers is from the Novartis Oncology Clinical Pharmacology internal memo: drug-drug interactions (DDI) database, Oct 2010, which is compiled primarily from the Indiana University School of Medicine's "Clinically Relevant" Table (<http://medicine.iupui.edu/flockhart/table.htm>), the University of Washington's Drug Interaction Database ([www.druginteractioninfo.org](http://www.druginteractioninfo.org)), and the FDA's "Guidance for Industry, Drug Interaction Studies"

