##### 4.4.1.2 Drugs that are metabolized by CYP450 enzymes

*In vitro* drug metabolism studies show that the metabolism of ceritinib is mediated by CYP3A4/5. Ceritinib is a time-dependent CYP3A4/5 inhibitor and is also a potent reversible inhibitor of CYP2A6, 2B6, 2C8, 2C9 and 3A4/5 and may consequently increase exposure to drugs metabolized by these enzymes. Clinical studies have not yet been performed to confirm the potential effect of ceritinib on substrate drugs metabolized by these enzymes in patients. Also, the potential effect of low and moderate CYP3A4/5 inhibitors and inducers on ceritinib clearance is not known.

Concomitant treatment of ceritinib with weak inhibitors or inducers of CYP3A4/5 is permitted. Caution is advised when ceritinib is co-administered with drugs that are moderate inhibitors or inducers of CYP3A4/5 (Appendix 1). Duration of concomitant treatment should be kept as short as possible, or completely avoided whenever possible. Patients receiving such medications must be monitored closely for any potentiation of toxicity or decrease of clinical benefit due to any individual concomitant medications, and may require dose titration or adjustment. Note that co-administration of ceritinib with strong inducers or inhibitors of CYP3A4/5 is prohibited (Section 4.4.2.5).

Concomitant treatment of ceritinib with medications known to be metabolized by CYP2A6, 2B6, 2C8 and 2C9 is allowed with caution (Appendix 1), except for drugs which have narrow therapeutic index/sensitive substrates for these CYP isoforms (Section 4.4.2.6 and Appendix 1).

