#### 4.4.2.5 Strong CYP3A inhibitors and inducers

*In vitro* metabolism studies suggest that oxidative metabolism of ceritinib is predominantly mediated by CYP3A4/5.

Strong inhibitors or inducers of CYP3A4/5 are prohibited. Patients receiving concomitant medications known to strongly inhibit and/or induce CYP3A4/5 that are deemed medically necessary should be excluded from the study. Refer to [Appendix 1](#) for a list of these medications. Please note that this list may not be comprehensive.

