#### 4.4.2.8 Medications that may prolong the QT interval or have a known risk of inducing Torsades de Pointes

Ceritinib has potent activity on the hERG channel with an IC50 of 0.4 μM. However, there were no ceritinib-related effects *in vivo* in monkeys at doses as high as 100 mg/kg (human equivalent dose (HED) of 1950 mg). Preliminary data from patients treated in the phase 1 study ([\[CLDK378X2101\]](#)) at doses of 50-750 mg suggest that ceritinib may have an effect on the QT interval. One patient (700 mg QD dose; <1%) had a QTc > 500 ms and 9 patients had an increase from baseline QTc > 60 ms.

Concomitant administration of ceritinib with drugs known to have a high risk of increasing the QTc interval and drugs known to increase the QTc interval that are also primarily metabolized by CYP3A4/5 should be avoided. Concomitant use of ceritinib and any medication included in [Appendix 1](#) titled "List of prohibited QT prolonging drugs" (i.e., drugs that are generally accepted by the Qtdrugs.org Advisory Board of the Arizona CERT to have a known risk of causing Torsades de Pointes) is not permitted.

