**Table 14-4 List of prohibited QT prolonging drugs**

Prohibited medications causing QTc prolongation			
Antiarrhythmic: amiodarone disopyramide dofetilide flecainide ibutilide procainamide quinidine*	Anticancer: arsenic trioxide vavdetanib	Antibiotic: azithromycin clarithromycin* erythromycin* moxifloxacin sparfloxacin	Antianginal: bepridil
	Antihistamine: astemizole* terfenadine*		Antipsychotic: chlorpromazine haloperidol* mesoridazine pimozide thioridazine
	Antimalarial: chloroquine halofantrine	Antinausea: domperidone droperidol	Opiate agonist: levomethadyl methadone
	Antilipemic: probucol	GI stimulant: cisapride*	
Antidepressant:	Anti-infective: pentamidine		

STU042015-076, [name], FormA-ResearchProtocol-V6, Mod\_19, 04-09-20 (1)

CONFIDENTIAL

This material is the property of the [UTSW Simmons Cancer Center](#). Do not disclose or use except as authorized in writing by the study sponsor.

citalopram			
------------	--	--	--

**Please note:** \*CYP3A substrate

Source: Arizona Center for Education and Research on Therapeutics (CERT), Drugs that prolong the QT interval and/or induce Torsades de Pointes, <http://www.azcert.org/medical-pros/drug-lists/drug-lists.cfm>

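### Table 14-2 gives caution status to seven drugs that Tables 14-1 or 14-4 prohibit, and section 7.1.3 allows for strong CYP3A inhibitors that section 4.4.2.5 and exclusion 10 bar

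*Combined protocol and SAP*

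**What the plan says.** Appendix 1 (section 13.1) contains four drug tables, three of which matter here.

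- Table 14-1 is titled "Prohibited medications that are strong inducers or inhibitors of CYP3A, or CYP3A substrates with narrow therapeutic index" and goes on to cover sensitive CYP2C substrates.
- Table 14-4 is titled "List of prohibited QT prolonging drugs".
- Table 14-2 is titled "List of medications to be used with caution". It is arranged by CYP class (2B6, 2C8, 2C9 and 3A4/5 substrates, then moderate 3A4/5 inhibitors and inducers), with proton pump inhibitors at the end.

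The body text sets the rules that these tables serve.

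- Section 4.4.2.5: "Strong inhibitors or inducers of CYP3A4/5 are prohibited". Patients taking such drugs "that are deemed medically necessary should be excluded from the study".
- Section 4.4.1.2 repeats the ban: "Note that co-administration of ceritinib with strong inducers or inhibitors of CYP3A4/5 is prohibited". The same section advises caution with moderate CYP3A4/5 inhibitors and inducers, citing Appendix 1, and says that giving substrates of four other CYP enzymes (2A6, 2B6, 2C8, 2C9) alongside ceritinib "is allowed with caution (Appendix 1), except for drugs which have narrow therapeutic index/sensitive substrates for these CYP isoforms".
- Section 4.4.2.8 says that concomitant use of any drug on the QT list, described as drugs generally accepted "to have a known risk of causing Torsades de Pointes) is not permitted".
- Exclusion 10 (section 3.3) excludes patients who cannot stop strong CYP3A4/5 inhibitors at least a week before ceritinib and stay off them for as long as they take part.
- Section 7.1.3 first says CYP3A inhibitors are to be avoided. It then says that where a strong one has to be given alongside ceritinib, the ceritinib dose is to be lowered. It gives no amount.

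**The concern.** A medication check should return one answer per drug. For some drugs Appendix 1 returns two, prohibited in one table and usable with caution in another, with no line saying which governs. Section 7.1.3 adds a second conflict, in operative text: it describes how to manage a combination that sections 4.4.1.2 and 4.4.2.5 forbid.

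What is at stake is patient safety. Section 4.4.2.5 says ceritinib's oxidative metabolism is mainly by CYP3A4/5. Section 7.1.2 says its QTc effect may depend on concentration, and section 4.4.2.8 reports potent activity on the hERG channel. A strong inhibitor or a second QT-prolonging drug is therefore what the bans are there to prevent. Someone who looks a drug up in Table 14-2 alone, or follows the conditional sentence in section 7.1.3, could give a banned drug.

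**Working it through.** The plan has no figure to reproduce. The check is a count of overlapping entries, followed by a comparison of texts.

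**Size of Table 14-2.** Cells by class, in table order: 6 (CYP2B6) + 5 (CYP2C8) + 12 (CYP2C9) + 30 (CYP3A4/5 substrates) + 14 (moderate inhibitors) + 8 (moderate inducers) + 5 (proton pump inhibitors) = 80. Ten names occur twice (methadone, torsemide, tolbutamide, efavirenz, ritonavir, erythromycin, dronedarone, casopitant, diltiazem, verapamil), so there are 80 − 10 = 70 distinct entries.

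**Overlap with the prohibited tables.**

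| Drug | Class in Table 14-2 | Cells | Prohibited by |
|---|---|---|---|
| clarithromycin | CYP3A4/5 substrate | 1 | 14-1 and 14-4 |
| telithromycin | CYP3A4/5 substrate | 1 | 14-1 |
| ritonavir | CYP3A4/5 substrate; moderate inducer | 2 | 14-1 |
| tipranavir | moderate inducer | 1 | 14-1 |
| erythromycin | CYP3A4/5 substrate; moderate inhibitor | 2 | 14-4 |
| haloperidol | CYP3A4/5 substrate | 1 | 14-4 |
| methadone | CYP2B6 substrate; CYP3A4/5 substrate | 2 | 14-4 |

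Table 14-1 accounts for 4 drugs, Table 14-4 for 4 and Table 14-3 for none. Clarithromycin is in both groups, so the union is 4 + 4 − 1 = 7 drugs. That is 7/70 = 10% of distinct entries, in 1 + 1 + 2 + 1 + 2 + 1 + 2 = 10 of the 80 cells.

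**Does the body text lead a reader to the caution status?** For four of the seven it does. Section 4.4.1.2 cites Appendix 1 for caution with moderate inhibitors and inducers, which reaches erythromycin, ritonavir and tipranavir. It also cites Appendix 1 for CYP2B6 substrates, which reaches methadone. Its exception covers narrow-therapeutic-index and sensitive substrates and does not mention QT risk, so it does not itself remove methadone. The other three appear in Table 14-2 only as CYP3A4/5 substrates.

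**Does the body text settle the status?** Yes, for all seven. Sections 4.4.1.2 and 4.4.2.5 ban the four strong inhibitors, and section 4.4.2.8 bans the four QT drugs.

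**Section 7.1.3 against section 4.4.2.5 and exclusion 10.** When a strong inhibitor is medically necessary, section 7.1.3 answers with a lower ceritinib dose. Section 4.4.2.5 answers with exclusion from the study. Section 7.1.3 cannot be read as an on-treatment exception to an entry rule, because exclusion 10 runs for the whole of participation and the ban in sections 4.4.1.2 and 4.4.2.5 is unconditional. The two instructions are incompatible.

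**The case against.** The strongest reply is that the protocol already supplies the answer. Section 4.4 opens by permitting necessary concomitant therapy except where it is specifically prohibited, and all seven drugs are prohibited by name. Table 14-2 is a pharmacological classification, as its footnote indicates, and one drug can fall in several CYP classes. It even lists anticancer agents such as cyclophosphamide and imatinib, which section 4.4.2.1 bars, so a listing cannot sensibly be permission. Section 4.4.2.8 names the prohibited QT table by title, section 4.4.2.5 points to the list of strong inhibitors and inducers, and exclusion 10 refers to the tables in the plural. An error needs a reader who consults one table and skips two others in a short appendix. On section 7.1.3, the sentence is conditional, follows an instruction to avoid, and sits among drug-information text.

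Much of this stands. The intended rule can be worked out, the overlap comes from cross-classification, and the entry counts say nothing about how often an error would occur. Two things are not answered. A table whose title assigns a conduct status, and which section 4.4.1.2 uses as the caution list, is wrong for these seven drugs whatever produced the overlap. And section 4.4's general clause does not reconcile section 7.1.3 with the ban, because section 7.1.3 speaks directly to the banned case and answers it differently.

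**Conclusion.** The concern holds on both parts and is minor. Seven drugs carry contradictory statuses within Appendix 1, and one sentence in section 7.1.3 contradicts the ban on strong CYP3A inhibitors. The prohibition is clearly meant to prevail, so a reader who applies section 4.4.2 will act correctly; the exposure is limited to someone relying on Table 14-2 or section 7.1.3 alone. The effect is on conduct and safety only.

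The count rests on one convention: a drug counts only if another Appendix 1 table names it. Entries barred only by section 4.4.2 text are outside the seven. These include the anticancer agents and possibly acenocoumarol, given the ban on coumadin derivatives in section 4.4.2.3.

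**What to change.** Add one line under Table 14-2 stating that any drug in Tables 14-1, 14-3 or 14-4, or barred by section 4.4.2, is prohibited regardless of its listing there. This is better than deleting the seven names, which would leave in place entries barred only by the body text.

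In section 7.1.3, replace the dose-reduction sentence with a reference to the ban in section 4.4.2.5.

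The cost is one line and one sentence, with no change to design, sample size or analysis.
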